6.1 General Considerations

Study Schedule of Events is presented in [Section 9.1](#).

Continuous variables will be summarized using the following descriptive summary statistics: the number of participants (n), mean, standard deviation (SD), median, minimum (min), and maximum (max).

Categorical variables will be summarized using counts and percentages.

For the summary statistics of all numerical variables unless otherwise specified, the display precision will follow programming standards. Variable display standards are presented in [Section 9.2](#).

When count data are presented, the percentage will be suppressed when the count is zero to draw attention to the non-zero counts. A row denoted "Missing" will be included in count tabulations where specified on the shells to account for dropouts and missing values. The denominator for all percentages will be the number of participants in that vaccination group within the analysis set of interest, unless otherwise specified.

Baseline value is defined as the most recent non-missing measurement (scheduled or unscheduled) collected before vaccine injection, unless otherwise specified. For immunogenicity tests and NP swab tests, the baseline is defined as the most recent non-missing result/measurement (scheduled or unscheduled) collected before or on the date (and time, if applicable) of injection (Day 1).

Age: unless otherwise specified, age is calculated as the age at screening. In the analyses for subgroups defined by age, age at screening will be used for derivation of age groups.

Vaccination groups:

The following vaccination groups will be used for summary purposes:

- mRNA-1010 50 ug
- Fluarix Quadrivalent 60 ug

All analyses and data summaries/displays will be provided by vaccination group using appropriate analysis population, unless otherwise specified. Summaries may also contain a display for all vaccination groups pooled together (i.e., overall group).

Study day relative to injection will be calculated as below:

- Study day prior to injection will be calculated as: date of assessment/event – date of injection.
- Study day on or after the date of injection will be calculated as: date of assessment/event – date of injection + 1.

Unscheduled visits: Unscheduled visit measurements will be included in analysis as follows:

- In scheduled visit windows per specified visit windowing rules
- In the derivation of baseline/last on-treatment values
- In the derivation of max/min on-treatment values and max/min change from baseline values for safety analyses
- In individual participant data listings as appropriate

Visit windowing rules: The analysis visit windows for protocol-defined visits are provided in [Section 9.3](#).

Analysis Periods:

The following analysis periods will be used for safety analyses in the study:

- 7 days post-vaccination: this period includes the day of vaccination and 6 subsequent days. This analysis period will be used for solicited local/systemic ARs and SAEs that occur during this time.
- Up to 28 days post-vaccination: this period starts from the day of vaccination and spans 28 days to include the day of vaccination and 27 subsequent days. This analysis period will be used for unsolicited AE, except for solicited AR, unless specified otherwise.
- Up to 180 days post-vaccination: this period starts from the day of vaccination and spans to 180 days to include the day of vaccination and 179 subsequent days. This analysis period will be used for MAAEs, SAEs, and AESIs
- Up to data cutoff date: this period starts from day of vaccination and continues through the data cut-off date applied at planned analyses as specified in [Section 6.8](#).
- Overall study period: this period starts on Day 1 and continues through the earliest of the following: study completion, discontinuation from the study, or death.

For the Day 29 primary analysis, the analysis will include all participants' immunogenicity data and safety data collected up to Day 29 post-vaccination. For the 6-months analysis, the analysis may include a subset of participants' immunogenicity data (the first 1000 randomized participants per study design) collected up to Day 181, vaccine efficacy data on Day 181/end of influenza season, and safety data up to 180 days post-vaccination. Additional details are presented in [Section 6.8](#).

Incomplete/missing data:

- Imputation rules for missing prior/concomitant medications, non-study vaccinations and procedures are provided in [Section 9.4](#).
- Imputation rules for missing AE dates are provided in [Section 9.4](#).
- For summarizations of GMTs, antibody titers reported as below the lower limit of quantification (LLOQ) will be replaced by 0.5 x LLOQ. Values that are greater than the upper limit of quantification (ULOQ) will be converted to the ULOQ.
- Other incomplete/missing data will not be imputed, unless otherwise specified.

Subgroups:

Table 5: Definition for Subgroups

Subgroup Variable	Categories
Age Group 1	≥ 18 to < 50 years old ≥ 50 to < 65 years old ≥ 65 years old
Age Group 2	≥ 18 to < 50 years old ≥ 50 to < 65 years old ≥ 65 to < 75 years old ≥ 75 years old
Influenza vaccine status in the prior 12 months	Received previous season flu vaccine Did not received previous season flu vaccine
Race	White Black or African American Asian American Indian or Alaska Native Native Hawaiian or Other Pacific Islander Other (combining Not Reported and Unknown)
Sex	Male Female
BMI (only for immunogenicity analyses)	$BMI < 30 \text{ kg/m}^2$ $BMI \geq 30 \text{ kg/m}^2$

6.2 Background Characteristics

6.2.1 Participant Disposition

The number of participants in the following categories will be summarized based on participants screened:

- Number of participants screened
- Number and percentage of screen failure participants and the reason for screen failure

The percentage of participants who screen failed will be based on the number of participants screened. The percentage of participants reporting each reason for screen failure will be based on the number of participants who screen failed. A separate listing will be provided for screen failure participants with reasons for screen failure. Participants with any inclusion and exclusion criteria violation will also be provided in a listing.

The number and percentage of participants in each of the following disposition categories will be summarized by vaccination group based on Randomization Set, Safety Set, Immunogenicity Set, and mITT Set.

- Received injection
- Completed study
- Prematurely discontinued the study and the reason for discontinuation

A participant disposition listing will be provided, including informed consent, participants who completed the study injection schedule, participants who completed study, participants who discontinued from participation in the study, with reasons for discontinuation. Randomization data will be provided in a listing.

The number and percentage of participants in the following categories (analysis sets defined in [Section 5](#)) will be summarized as defined in [Section 6.1](#) (for general consideration) based on the Randomized set:

- Randomization Set
- Full Analysis Set
- mITT Set
- PP Set for Efficacy
- Immunogenicity Set
- PP Immunogenicity Set
- Safety Set
- Solicited Safety Set

The denominators of the percentages will be based on participants in the Randomization Set, unless otherwise specified.

A separate summary table will include the number and percentage of randomized participants by stratification factors as randomized via IRT and actual stratification factors derived from eCRF for each vaccination group and overall. Additionally, a comparison table between IRT randomization stratum and eCRF derived stratum will be provided.

6.2.2 Demographics and Baseline Characteristics

Descriptive statistics will be calculated for the following continuous demographic and baseline characteristics:

- Age (years)
- Weight (kg)
- Height (cm)
- Body mass index (BMI) (kg/m^2)
- EFS total score (for participants aged 65 years and older)

The number and percentage of participants will be provided for the following categorical variables:

- Age group 1 (18 to < 50 years old, ≥ 50 to < 65 years old, or ≥ 65 years old) per eCRF
- Age group 2 (18 to < 50 years old, ≥ 50 to < 65 years old, ≥ 65 to < 75 years old, or ≥ 75 years old) per eCRF
- Sex (Male, Female)
- Race (White, Black or African American, Asian, American Indian or Alaska Native, Native Hawaiian or Other Pacific Islander, Other, Not Reported, Unknown)
- Ethnicity (Hispanic or Latino, Not Hispanic or Latino, Not Reported, Unknown)
- Country
- Influenza vaccine status in the prior 12 months at the time of screening (received previous season influenza vaccine or not received previous season influenza vaccine) per eCRF
- EFS total score category (Fit: 0-3, Vulnerable: 4-5, Frail: 6 or more)

The summaries will be provided separately for all analysis sets (except Solicited Safety Set) defined in the [Section 5](#).

6.2.3 Medical History

Medical history data will be coded by system organ class (SOC) and preferred term (PT) using the Medical Dictionary for Regulatory Activities (MedDRA) version 25.0 or higher.

The number and percentage of participants with any medical history will be summarized by SOC and PT for Safety Set. A participant will be counted only once for multiple events within each SOC and PT. SOC will be displayed in an internationally agreed order. PT will be displayed in descending order of frequency of mRNA-1010 vaccination group and then alphabetically within each SOC. All the medical history data will be presented in a listing.

6.2.4 Prior and Concomitant Medications and Vaccinations

Prior and concomitant medications and non-study vaccinations will be coded using the WHO drug dictionary (WHODD) version Mar 2022. Imputation rules for missing dates of medications and non-study vaccinations are detailed in [Section 9.4](#). The summary of concomitant medications will be based on the Safety Set.

Categorization of prior and concomitant medications are summarized in [Table 8](#) in [Section 9.5](#). An overall summary of medications and non-study vaccinations including the number and percentage of participants who take the following will be presented by vaccination group:

- Prophylactic antipyretics or analgesics medication up to 28 days post-injection
- Any concomitant medications and non-study vaccinations up to 28 days post-injection
- Non-study seasonal influenza vaccine up to 28 days post-injection
- Systemic steroids (≥ 10 mg/day prednisone or equivalent), immunosuppressants, immune-modifying drugs, immunoglobulins, and/or blood products administered at any time up to 28 days post-injection

The number and percentages of participants with at least one concomitant medication will be summarized by preferred terms and vaccination group. Prior, concomitant medications and non-study vaccination will be presented in a listing. Medications taken to prevent or treat pain or fever will also be presented in a listing. Concomitant procedures will be presented in a listing.

6.2.5 Protocol Deviations

The study protocol deviations will be reviewed on a regular basis and categorized in “Significant” and “Non-significant” based on the impacts on study results. Significant protocol deviations are a subset of protocol deviations that may significantly impact the completeness,

accuracy, or reliability of the study data or that may significantly affect a participant's rights, safety, or well-being. Significant protocol deviations rules will be developed and finalized before database lock.

The number and percentage of the participants with each significant protocol deviation type will be summarized by vaccination group and total based on the Randomization Set.

Significant protocol deviations that impact critical or key study data will be determined and documented by Sponsor prior to database lock and unblinding. Participants with such significant protocol deviations will be excluded from the PP analyses. Reasons of exclusion from PP analyses will be summarized.

Significant protocol deviations will be summarized in a table and presented in a listing.

6.2.6 Study Exposures

The number and percentage of participants received vaccine injection at Day 1 visit, study duration ≥ 7 days after vaccine injection, study duration ≥ 28 days after vaccine injection and study duration ≥ 180 days after vaccine injection as well as the study duration from vaccine injection to the EoS will be summarized by vaccination group and overall for Safety Set. Study vaccine administration data will be presented in a listing. Participants who had dosing errors will be presented in a separate listing.

6.3 Immunogenicity Analysis

For immunogenicity analysis, antibody titers reported as below the LLOQ will be replaced by $0.5 \times$ LLOQ. Values that are greater than the ULOQ will be converted to the ULOQ.

The primary analysis population for immunogenicity will be the PP Immunogenicity Set, unless specified otherwise. In addition, the first 1000 randomized participants will also provide blood samples at Day 181 and Day 361 (Month 12), a subset of which will be used for immunogenicity analysis.

6.3.1 Analysis of Co-primary Immunogenicity Endpoints

There are four co-primary endpoints based on GMR and SCR differences for the two vaccine-matched A strains, and four co-primary endpoints based on GMR and SCR differences for the two vaccine-matched B strains. The primary objective of this study is to use the immunogenicity

response to infer efficacy in participants receiving mRNA-1010. The primary immunogenicity estimands are presented in detail in [Table 12](#). The Day 29 primary analysis of immunogenicity will be performed after all participants have completed the Day 29 visit.

6.3.1.1 Primary Analysis

- Analysis of GMTs of anti-HA antibodies as measured by HAI against vaccine-matched influenza A and B strains at Day 29

An analysis of covariance model (ANCOVA) will be performed using the log-transformed HAI titers against a specific vaccine-matched strain at Day 29 as the dependent variable, vaccination group as the fixed variable, log-transformed baseline HAI titers as a fixed covariate, adjusting for the stratification factors. The geometric least square mean (GLSM), and its corresponding 95% CI results in log-transformed scale estimated from the model will be back-transformed to obtain these estimates in the original scale, as an estimate of the GMT for each vaccination group.

The GMR for mRNA-1010 vs. active comparator, estimated by the ratio of GLSM and the corresponding 2-sided 97.5% CI will be provided to assess the vaccine difference and calculated by back-transforming of the difference estimated from the ANCOVA model. The corresponding 2-sided 97.5% CI of GMR will be provided to assess the difference in immune response between the mRNA-1010 compared to the active comparator group at Day 29. For each strain, the non-inferiority of GMT will be considered demonstrated if the lower bound of the 97.5% CI of the GMR is > 0.667 based on a non-inferiority margin of 1.5. Refer to Immune Estimand 1a in [Table 12](#).

Descriptive statistics (n, median, min, max) will also be provided for the GMT of HAI titers with corresponding 95% CI at each timepoint. The 95% CIs will be calculated based on the t-distribution of the log-transformed values then back transformed to the original scale for presentation. In addition, the GMT with corresponding 95% CI will be plotted at each time point respectively.

- Analysis of SCR against vaccine-matched influenza A and B strains as measured by HAI at Day 29

The number and percentage of participants with seroconversion due to vaccination will be provided with 2-sided 95% CI using the Clopper-Pearson method at Day 29. To compare the

seroconversion rates between the vaccination groups, the Miettinen-Nurminen's method will be used to calculate the 97.5% CI for the difference in SCR. Refer to Immune Estimand 2a in [Table 12](#). For each strain, the non-inferiority of SCR will be considered demonstrated if the lower bound of the 97.5% CI of the SCR difference is $> -10\%$ based on a non-inferiority margin of 10%.

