9.5.1 Immunogenicity Analyses

The primary analysis population for immunogenicity will be the PP Immunogenicity Set, unless specified otherwise. The primary objective of this study is to use the immunogenicity response to infer efficacy in participants receiving mRNA-1010.

Immune responses, as measured by GMT and seroconversion rate in the mRNA-1010 group based on Day 29 HAI titers, will be compared to that in participants receiving the active comparator for all 4 strains.

An analysis of covariance model (ANCOVA) will be carried out. The model will include the log-transformed HAI titers at Day 29 as the dependent variable, vaccination group as the fixed variable, log-transformed baseline HAI titers as a fixed covariate, adjusting for the stratification factors. The geometric least square mean (GLSM), and its corresponding 95% CI results in log-transformed scale estimated from the model will be back-transformed to obtain these estimates in the original scale, as an estimate of the GMT. GMR, estimated by the ratio of GLSM and the corresponding 2-sided 97.5% CI will be provided to assess the treatment difference. The corresponding 2-sided 97.5% CI of GMR will be provided to assess the difference in immune response between the mRNA-1010 compared to the active comparator group at Day 29. For each strain, the noninferiority of GMT will be considered demonstrated if the lower bound of the 97.5% CI of the GMR is > 0.667 based on a noninferiority margin of 1.5.

The number and percentage of participants with seroconversion due to vaccination will be provided with 2-sided 95% CI using the Clopper-Pearson method at Day 29. To compare the seroconversion rates between the vaccination groups, the Miettinen-Nurminen's method will be used to calculate the 97.5% CI for the difference in seroconversion rates. The seroconversion rate difference with the corresponding 97.5% CI at Day 29 will be provided. For each strain, the noninferiority of seroconversion rate will be considered demonstrated if the lower bound of the 97.5% CI of the seroconversion rate difference is $> -10\%$ based on a noninferiority margin of 10%.

The primary analyses will be repeated using the Immunogenicity Set as a sensitivity analysis.

Subgroup analysis for the coprimary immunogenicity endpoints will be conducted as appropriate.

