4.3 Sample Size and Power

Approximately 6,000 participants will be randomly assigned to vaccine in this study in a 1:1 ratio to receive either mRNA-1010 or an active comparator. With approximately 3,000 participants exposed to mRNA-1010, the study has approximately 95% probability to observe at least 1 participant with an AE at a true 0.1% AE rate.

Assuming approximately 15% of randomized participants will be excluded from the PP Immunogenicity Set, with approximately 5100 participants in the PP Immunogenicity Set (1:1 ratio; approximately 2550 in each vaccine group), this will provide at least 95% power to demonstrate non-inferiority of the immune response in all 4 strains, as measured by the GMT in participants receiving mRNA-1010 compared with that in the active comparator group, at a 2-sided alpha of 0.025 level, assuming an underlying GMR of 0.9 in all 4 strains and a non-inferiority margin of 1.5. The standard deviation of the natural log-transformed levels is assumed to be 1.5.

This sample size will also provide at least 95% power to demonstrate non-inferiority of the immune response in all 4 strains as measured by SCR in the mRNA-1010 group compared with that in the active comparator group, at a 2-sided alpha of 0.025 level, assuming a SCR of 70% in influenza A strains and 60% in influenza B strains, respectively, in the mRNA-1010 group (a

true rate difference is 0 compared to the active comparator group), and a non-inferiority margin of 10%.

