4.4 Randomization

Randomization will be performed using a centralizing interactive response technology (IRT). and stratified by age categories (18 to < 50 years old, ≥ 50 to < 65 years old, or ≥ 65 years old) and influenza vaccine status in the prior 12 months (received or did not receive) at the time of screening. At least 50% of enrollees will be ≥ 50 years old, including approximately 20% who will be ≥ 65 years old. The Sponsor anticipates approximately 300 participants will be ≥ 75 years old.

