6.3.2 Analyses of Secondary Immunogenicity Endpoints

- Analysis of GMTs of anti-HA antibodies as measured by HAI against vaccine-matched influenza A strains on Day 29 (superiority and super-superiority testing)

If the non-inferiority is demonstrated for A strains only, superiority of mRNA-1010 relative to the active comparator against vaccine-matched influenza A strains at Day 29 will be tested at a two-sided $\alpha_1=2.5\%$ level. If the non-inferiority is demonstrated for both A and B strains, superiority of mRNA-1010 relative to the active comparator against vaccine-matched influenza A strains at Day 29 will be tested at a two-sided $\alpha_1=5\%$ level.

The same ANCOVA model for primary analysis will be applied. The superiority of GMT in participants who received mRNA-1010 compared to GMT in participants who received active

comparator will be demonstrated by the lower bound of the $(100\% - \alpha_1)$ CI % of the GMR ruling out 1 (lower bound > 1).

If superiority is demonstrated based on lower bound of $(100\% - \alpha_1)$ CI % of $GMR > 1$, the super-superiority of GMT in participants who received mRNA-1010 compared to participants who received active comparator will then be evaluated based on a lower bound of $(100\% - \alpha_1)$ CI % of the $GMR > 1.5$.

- Analysis of SCRs of anti-HA antibodies as measured by HAI against vaccine-matched influenza A strains on Day 29 (super-superiority testing)

Rate of seroconversion is defined as the proportion of participants with either a pre-vaccination HAI titer $< 1:10$ and a post-vaccination titer $\geq 1:40$ or a pre-vaccination HAI titer $\geq 1:10$ and a minimum 4-fold rise in post-vaccination HAI antibody titer. If super-superiority has been demonstrated based on GMT, the SCR of the vaccine-matched influenza A strains at Day 29 between the vaccination groups will be compared. The Miettinen-Nurminen's method will be used to calculate the $(100\% - \alpha_1)$ CI for the difference in SCRs. For the A strains, the super-superiority of SCR will be considered demonstrated if the lower bound of the $(100\% - \alpha_1)$ CI % of SCR difference is $> 10\%$.

In addition, the number and percentage of participants that reached seroconversion at each time point will be provided with 2-sided 95% CI using the Clopper-Pearson method.

- Analysis of frequency of participants with an HAI titer $\geq 1:40$ on Day 29

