Target Population	Adults aged 18 years or older who receive the assigned IP administration, complied with immunogenicity blood sampling to have a baseline and at least 1 post-injection serum antibody assessment as measured by HAI assay after the IP administration, and have no significant protocol deviations impacting the immune response and RT-PCR-confirmed influenza between Days 1 to 29.	Adults aged 18 years or older who receive any IP administration and complied with immunogenicity blood sampling to have a baseline and at least 1 post-injection antibody assessment as measured by HAI assay.
Endpoint	GMT ratio of anti-HA levels on Day 29	As per Estimand 1a.
Treatment Conditions	mRNA-1010 vs. active comparator (Fluarix Tetra)	As per Estimand 1a.

Population-Level Summary	Immune response to seasonal influenza defined as GMT ratio of anti-HA level as measured by HAI assay using an ANCOVA model on the log-transformed tiers on Day 29, with the vaccination group as the fixed variable, adjusted for stratified age group used for randomization and log-transformed baseline tiers.	As per Estimand 1a.
Intercurrent Event Strategy		
IcEv1 (early discontinuation or unrelated death)	Principal stratum	Principal stratum
IcEv2 (alternative influenza vaccine)	Principal stratum	Treatment policy
IcEv3 (COVID-19 vaccine)	Principal stratum	Treatment policy
IcEv4 (prohibited medications)	Principal stratum	Treatment policy
IcEv5 (early infection)	Principal stratum	Treatment policy
IcEv6 (wrong vaccination)	Principal stratum	Treatment policy

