Estimand Description	Immune response to influenza measured as seroconversion rate difference of antibody using HAI assay on Day 29 in adults aged 18 years or older who receive IP administration and complied with immunogenicity blood sampling to have a baseline and at least 1 post-injection antibody assessment without significant protocol deviations impacting immune response and RT-PCR-confirmed influenza between Days 1 to 29.	Immune response to influenza measured as seroconversion rate difference of antibody using HAI assay on Day 29 in adults aged 18 years or older who receive IP administration irrespective of any significant protocol deviations impacting immune response and complied with immunogenicity blood sampling to have a baseline and at least 1 post-injection antibody assessment.
Target Population	Adults aged 18 years or older who receive the assigned IP administration, complied with immunogenicity blood sampling to have a baseline and at least 1 post-injection antibody assessment after the IP administration, and have no significant protocol deviations impacting the immune response.	Adults aged 18 years or older who receive any IP administration and complied with immunogenicity blood sampling to have a baseline and at least 1 post-injection antibody assessment.
Endpoint	Seroconversion rate difference of antibody measured by HAI assay on Day 29.	As per Estimand 2a.
Treatment Conditions	mRNA-1010 vs. active comparator (Fluarix Tetra)	As per Estimand 2a.
Population-Level Summary	Immune response to influenza defined as seroconversion rate difference of antibody using Miettinen-Nurminen's method.	As per Estimand 2a.
Intercurrent Event Strategy		

IcEv1 (early discontinuation or unrelated death)	Principal stratum	Principal stratum
IcEv2 (alternative influenza vaccine)	Principal stratum	Treatment policy
IcEv3 (COVID-19 vaccine)	Principal stratum	Treatment policy
IcEv4 (prohibited medications)	Principal stratum	Treatment policy
IcEv5 (early infection)	Principal stratum	Treatment policy

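### The seroconversion comparisons name Miettinen-Nurminen without strata; using the randomisation strata is a free, modest gain in precision that matters mainly for the last test, H5

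*SAP*

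**What the plan says.** Randomisation uses three age groups and "influenza vaccine status in the prior 12 months (received or did not receive) at the time of screening" (SAP 4.4), which makes six strata.

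The GMT co-primary endpoint is analysed by ANCOVA with "log-transformed baseline HAI titers as a fixed covariate, adjusting for the stratification factors" (SAP 6.3.1.1).

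The SCR comparison is defined in four places, none of which gives strata or weights:

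- SAP 6.3.1.1, co-primary endpoints: "the Miettinen-Nurminen's method will be used to calculate the 97.5% CI for the difference in SCR".
- SAP 6.3.2, H5: "The Miettinen-Nurminen's method will be used to calculate the" interval at the level passed down the hierarchy.
- SAP 9.8, Table 12, Estimand 2a: "seroconversion rate difference of antibody using Miettinen-Nurminen's method".
- Protocol 9.5.1: "the Miettinen-Nurminen's method will be used to calculate the 97.5% CI for the difference in seroconversion rates".

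SAP 6.2.1 tabulates the strata both as randomised in the IRT and as derived from the eCRF, but does not link either to the SCR analysis.

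**The concern.** The method has a crude two-group form and a stratified form, and the plan does not say which is meant. Programmed as written, it gives the crude difference. After stratified randomisation the crude interval ignores that the strata are balanced between groups. If the strata predict seroconversion, the stated variance is too large and the interval somewhat conservative.

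Validity is not at stake, because type I error is not inflated. Precision is, and it counts most at H5, where the lower bound must exceed 10 points for both A strains. If the true difference is only a few points above 10, a small change in width can decide the result. The unstated form also leaves a programming choice open in a co-primary analysis.

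**Working it through.** **Inputs from the documents.** 2550 per group in the PP Immunogenicity Set; two-sided level 0.025 for non-inferiority; margin 10 points; true difference 0; power "assuming a SCR of 70% in influenza A strains and 60% in influenza B strains" (SAP 4.3). H5 is tested at 5% or 2.5% (SAP 6.5). Age shares are taken as 0.50/0.30/0.20, from at least half aged 50 or over and about 20% aged 65 or over (SAP 4.4).

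**Assumptions.** Previously vaccinated share 0.35; additive stratum effects; the spreads below. The documents give none of these.

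**1. The plan's own power figure.** Power = Φ(0.10/SE − 2.241), with SE = √(2p(1−p)/2550).

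- p = 0.70: SE = 0.01283; Φ(7.79 − 2.24) = 0.99999999.
- p = 0.60: SE = 0.01372; Φ(7.29 − 2.24) = 0.9999998.

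The stated floor of 95% is met with great room to spare, so stratifying changes nothing at this step.

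**2. Width.** With fixed, balanced strata, the variance per person falls from p(1−p) to p(1−p) − B, where B is the between-stratum variance of the rates. The crude/stratified width ratio is √[p(1−p)/(p(1−p) − B)].

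For spreads of 20 points by age (0, −10, −20) and 15 by prior vaccination:

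- Age: 0.3×0.10² + 0.2×0.20² − 0.07² = 0.00610.
- Vaccination: 0.15²×0.35×0.65 = 0.00512.
- B = 0.01122, and √(0.21/0.19878) = 1.028.

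| Spread, age/vaccination (points) | B | Crude wider at 70%: formula (score interval) | Same at 60% | 97.5% half-width at 70%, crude → stratified | Same at 60% |
|---|---|---|---|---|---|
| 10/10 | 0.00380 | 0.9% (0.9%) | 0.8% (0.8%) | 2.88 → 2.85 | 3.07 → 3.05 |
| 20/15 | 0.01122 | 2.8% (2.7%) | 2.4% (2.4%) | 2.88 → 2.80 | 3.07 → 3.00 |
| 30/20 | 0.02283 | 5.9% (5.8%) | 5.1% (5.0%) | 2.88 → 2.72 | 3.07 → 2.93 |

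The figures in brackets come from solving the crude and stratified score intervals numerically. With equal rates in all strata the ratio is 0.9995, a penalty of 0.05% of width.

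**3. H5.** Assume a comparator rate of 60% and a true difference of 13 points. The crude SE is √((0.24 + 0.1971)/2550) = 0.01309. The actual standard deviation is √((0.4371 − 2B)/2550), which is 0.01275 in the middle case. At 5%:

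- Crude: Φ((0.03 − 1.960×0.01309)/0.01275) = 63.3%.
- Stratified: Φ(0.03/0.01275 − 1.960) = 65.3%.

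Simulated per-strain power (200,000 runs, normal-approximation variances):

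| Spread | α = 5%, crude → stratified | α = 2.5%, crude → stratified |
|---|---|---|
| 10/10 | 63.0 → 63.8% | 51.9 → 52.7% |
| 20/15 | 63.3 → 65.4% | 52.1 → 54.6% |
| 30/20 | 63.7 → 67.9% | 52.2 → 57.4% |

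At a true difference of 15 points, the gains by the same formula are about 0.1, 0.3 and 0.5 points (α = 5%) and 0.2, 0.6 and 1.1 points (α = 2.5%).

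**4. Type I error and target.** A separate simulation applied the score tests themselves, with a 40% vaccinated share. At a true difference of exactly 10 points (one-sided nominal 0.025), the crude test rejected in 0.022 of runs when strata ranged over 50–80%, and in 0.019 when they ranged over 37–87%. The stratified test rejected in about 0.025. Under 1:1 allocation the weight n1·n0/(n1+n0) is close to a quarter of the stratum size, so both forms estimate practically the same overall difference.

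**The case against.** The strongest reply is that nothing in the plan is wrong. The crude interval is valid, four passages agree, and Table 12 states adjustment where it is meant: Estimand 1a is "adjusted for stratified age group used for randomization and log-transformed baseline tiers", while Estimand 2a mentions none. The natural reading is therefore the crude interval. That is fair, and it makes this an efficiency point rather than an error.

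The size is also conditional. The widest case needs strata running from 37.5% to 87.5%. Exclusion criterion 12 bars influenza vaccination within 180 days before Day 1, so the vaccinated stratum could be small. With a 5% share, the crude interval at 70% would be only about 0.5%, 1.7% and 3.9% wider in the three cases. A true difference of 13 points lies near the peak of the gain. H5 is reached only after H1, H3 and H4 succeed, and it needs both A strains, so the effect on the trial's overall outcome is smaller than the per-strain figures. All of this stands, and it limits the benefit.

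The practical objections weigh less. SAP 6.3.1.3 applies the primary methods to subgroups, where some of the six strata will be empty, but an empty stratum gets zero weight under n1·n0/(n1+n0). A protocol edit is not essential, because SAP section 1 lets the SAP prevail.

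**Conclusion.** The point holds, as a minor one. No passage defining the SCR comparison gives strata or weights, although the trial randomises within six strata and adjusts the GMT analysis for the stratification factors. The crude interval is valid and at worst slightly conservative, and the non-inferiority conclusions are unaffected under the design assumptions.

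The gain is modest: none if the strata do not predict seroconversion, and about 1 to 6% of interval width at an SCR of 70% under the assumed spreads. For H5 it is about 1 to 5 points of per-strain power at a true difference of 13 points. The omission is certain. The size of the gain rests on assumed stratum rates and an assumed vaccinated share.

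**What to change.** Before unblinding, amend SAP 6.3.1.1 and 6.3.2 to:

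- specify the stratified Miettinen-Nurminen interval over the six randomisation strata for the SCR co-primary endpoints and H5;
- state the weights, for example n1·n0/(n1+n0) per stratum;
- state that strata as randomised in the IRT are used;
- give a rule for pooling small strata;
- keep the unstratified interval as a sensitivity analysis.

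Align Estimand 2a in Table 12, and Protocol 9.5.1 when it is next amended. The same edit can settle a separate mismatch: Estimand 1a adjusts for age group only, whereas SAP 6.3.1.1 adjusts for all the stratification factors. If the crude form is intended, one sentence saying so closes the specification gap.

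The cost is SAP wording and a standard software option. The strata are already recorded, and no participants, visits or data are added.
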